### ***Aim of this study:***

Demonstrate that **intraoperative NOL-guided titration of fentanyl improves initial recovery characteristics**. All times below are relative to when sevoflurane anesthesia is discontinued.

**Primary hypothesis.** Pain scores (0-10 verbal response scale) at 10-minute intervals during the initial 60 minutes of recovery are less in patient with NOL-guided fentanyl than with routine care, with 1 point being considered a clinically meaningful difference

**Primary Outcome.** Pain Scores at 10-minute intervals during the initial 60 minutes of recovery

**Secondary hypothesis.** NOL patients are more likely to have a “good” pain scores, defined as < 5 (i.e., 0,1,2,3 or 4) across the measured intervals, with a relative 10% or more increase in the proportion of good scores being considered clinical meaningful.

**Secondary Outcome.** Whether or not the pain score at any measured interval is < 5.

We will also consider several exploratory hypotheses.

**Exploratory hypothesis 1.** Fewer analgesic rescue boluses are required in NOL-titrated patients during the initial 60 minutes of recovery.

**Exploratory hypothesis 2.** NOL-guided patients are no less alert (Ramsay score) during the initial 60 minutes of recovery than those given fentanyl per routine, based on a clinically meaningful non-inferiority delta of 20%.

**Exploratory hypothesis 3.** Emergence from anesthesia (discontinuation of sevoflurane anesthesia to extubation) is faster in NOL-guided patients.

**Exploratory hypothesis 4.** Fewer NOL-guided patients experience post-operative nausea and/or vomiting (PONV) **at least once** during the initial 60 minutes of recovery.

**Exploratory hypothesis 5.** There are fewer episodes of inadequate analgesia (too much or too little) in NOL-guided patients. Inadequate analgesia will be defined by systolic pressure  $\geq 140$  mmHg, heart rate exceeding 90 beats/min, diaphoresis, tearing, or movement. Excessive anesthesia will be defined by MAP  $< 65$  mmHg or BIS  $< 40$ . All values must return to normal for at least 15 minutes for a subsequent deviation to be

considered a new episode. The outcome for a patient will be the number of episodes.

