## **Protocol**

Patients will be premedicated with 0-2 mg midazolam per preference of the attending anesthesiologist. General anesthesia will be induced as preferred by the attending anesthesiologist, usually with a combination of lidocaine 1 mg/kg, propofol 1-4 mg/kg, fentanyl 1-2 µg/kg, and rocuronium 0.6-1.2 mg/kg or succinylcholine 1.5 mg/kg, as clinically appropriate. The trachea will be intubated and the lungs will be mechanically ventilated per clinical routine. General anesthesia will be maintained with sevoflurane at a target concentration of 0.7 %, with the dose being adjusted based on apparent clinical need, supplemented with fentanyl. Sevoflurane will be given per clinical routine and adjusted as usual in response to vital signs, surgical need, etc. Nitrous oxide will not be used for induction or during anesthetic maintenance. Vasopressors, antihypertensives, and drugs to control heart rate may be given as clinically indicated. Depth of anesthesia will be recorded for all patients using BIS.

Unless another opioid is clinically indicated, fentanyl will be the only opioid used for induction and throughout anesthesia. Long-acting opioids such as morphine will not be given. No opioid will be given unless clinically indicated from the end of surgery until patients reach the recovery unit.

Patients will be randomized 1:1, stratified for pre-operative chronic opioid use, with random-sized blocking to NOL guided analgesic management or routine care. The randomization table will be prepared by trial statisticians, and allocation will be concealed until shortly before anesthetic induction with a web-based randomization system.

- 1) **Routine opioid management.** Clinicians will be blinded to NOL monitoring and use clinical judgement to determine how much fentanyl should be given, and when. Clinical judgement will be according to their standard practice and may include interpretation of blood pressure, heart rate, diaphoresis, tearing, and pupil size. Boluses of fentanyl 1 µg/kg actual body weight (ABW), up to a maximum dose of 100 µg per bolus, can be given per clinical judgement.  
**Towards the end of the surgery (approximately 30-45 minutes before end of surgery, based on clinical judgment), the boluses of fentanyl will be reduced to 0.5 µg/kg ABW, up to a maximum of 50 µg per boluses. Boluses will be given per clinical judgment.**

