## **Measurements**

Demographic and morphometric characteristics will be recorded, including sex, age, race, height, weight and opioid use in the last month (estimated morphine equivalents). Anesthesia clinicians cannot be blinded since they will need to titrate opioid administration to NOL. However, all postoperative care and evaluations will be fully blinded to randomization, thus preventing measurement bias. There will thus be separate teams of investigators for the intraoperative and postoperative portions of the trial.

All routine anesthetic monitoring will be used, and the results recorded electronically. Blood pressure will be evaluated continuously with an arterial catheter if clinically indicated; otherwise, blood pressure will be evaluated oscillometrically at 3-

minute intervals. Anesthetic drugs including end-tidal sevoflurane concentration, type and duration of surgery will also be recorded electronically at one-minute intervals. Inadequate analgesia will be defined by systolic pressure  $\geq 140$  mmHg, heart rate exceeding 90 beats/min, MAP  $< 65$  mmHg. Vasoactive drugs and episodes and duration of hypotension (mean arterial pressure  $< 65$  mmHg, occurrences of MAP  $< 60$  & MAP  $< 55$ ) will be recorded. Muscle-relaxant administration will be recorded as well.

During surgical stimulation under general anesthesia, a NOL of zero indicates no nociceptive response, and NOL of 100 indicates extreme nociceptive response. NOL values below 25 represent nociception/anti-nociception balance, suggesting either no nociception in the absence of noxious stimuli, or effective analgesia in the presence of noxious stimuli. NOL values are recorded by the Medasense monitor at 5-second intervals.

The clock on the NOL monitor will be synchronized to that driving the electronic record. Nociception will be continuously evaluated in all participating patients. However, values will be blinded to clinicians when patients are assigned to the routine opioid management group.

We will record the time of reversal agent administration wrist, the time at which sevoflurane is discontinued, along with the end of surgery (last stitch), eye opening, and extubation. Discontinuation of sevoflurane will be considered the end of anesthesia and the beginning of recovery.

The following will be recorded on the PMD-200 monitor, using the EVENTS button, as accurately as possible:

1. Medications administration:
  - a. Fentanyl
  - b. Vasoactive drugs

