## ***Data Analysis***

Randomized groups will be assessed for balance on baseline characteristics using the standardized differences, defined as the difference in means or proportions divided by the pooled standard deviation. An absolute standardized differences  $> 0.10$  will be considered as imbalanced. We will use modified intent-to-treat such that all randomized patients receiving any of the study intervention (either one, even if the incorrect treatment was applied) will be included in the primary analyses.

**Primary outcome.** We will assess the treatment effect of NOL guided analgesic management versus routine care on mean pain score with the first 60 minutes of the recovery period using a linear mixed effects model adjusting for within-patient correlation across the 7 time points, and fixed effects for intervention, time (as categorical) and the stratification variable of pre-operative chronic opioid use. We will also assess the treatment-by-time interaction. We will decide on the most appropriate correlation structure empirically, using the AIC criterion, and considering either AR(1), exchangeable, or other correlation.

**Sensitivity analysis.** As a sensitivity analysis we will assess the treatment effect on pain score using a mixed effects proportional odds model in which we consider patient as a random effect while estimating the proportional odds ratio for patients having a better outcome on NOL than standard care, again adjusting for the stratification variable.

**Secondary outcome.** We will assess the treatment effect of NOL versus routine care on the proportion of patients with pain score less than 5 (i.e., 0-4) across the 7 time points using a generalized linear mixed effects model with a binary outcome ( $<5$  or  $\geq 5$ ), log link

(to be able to estimate relative risk), patient as random effect and modeling the within-subject serial correlation using an R matrix (considering autoregressive AR(1), exchangeable and unstructured correlation structures), with treatment group and the stratification variable as fixed effects. We will also assess the treatment-by-time interaction. Results will be reported as the relative risk (95% CI) of having a “good” pain score over time in NOL versus routine care.

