**Exploratory outcome 1.** We will assess the treatment effect on the first exploratory outcome of number of analgesic rescue boluses using either a negative binomial regression (for count data), or else a proportional odds logistic regression if the negative binomial distribution is not a good fit to the data. In either case we will again adjust for the stratification variable.

**Exploratory Outcome 2.** We will assess the treatment effect on the Ramsey score measured at 10 minute intervals for during the first 60 minutes using a mixed effects proportional odds model to adjust for the within-patient correlation in the same manner as described for the sensitivity analysis for the primary outcome. We will test whether NOL is noninferior to routine care on the Ramsey score using a noninferiority delta of 1.2 for the proportional odds ratio, such that NOL will be deemed noninferior if the upper confidence limit for the odds ratio is less than 1.2. This will be accompanied by a 1-sided statistical test for noninferiority using the method described in Mascha and Sessler (2011), in which we use the parameter estimate and standard error of the treatment effect from the mixed effects model as well as the noninferiority delta in the test statistic, as

$$T_{NI} = \frac{\hat{\beta}_1 - \delta}{SE_{\hat{\beta}_1}}, \text{ where } \hat{\beta}_1 \text{ is the estimated log-odds ratio, } SE_{\hat{\beta}_1} \text{ is the estimated standard error, and } \delta \text{ is}$$

the log (delta), or log (1.2).

**Exploratory Outcome 3.** We will assess the treatment effect (in form of a hazard ratio) on the time to emergence from anesthesia using a Cox proportional hazards regression model adjusting for the stratification variable. We will check the proportional hazards assumption graphically and with the treatment-by-log (time) interaction. In presence of an interaction the treatment effect will be assessed using the log-rank test from a Kaplan-Meier analysis.

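### If proportional hazards fails for emergence time, the fallback log-rank test drops the stratification factor and gives no effect size, so faster emergence is tested but not quantified

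*Combined protocol and SAP*

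**What the plan says.** The hypothesis is directional. Exploratory hypothesis 3, under Aim of this study, reads: "Emergence from anesthesia (discontinuation of sevoflurane anesthesia to extubation) is faster in NOL-guided patients".

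The main analysis (Data Analysis, Exploratory Outcome 3) names its effect measure: "We will assess the treatment effect (in form of a hazard ratio) on the time to emergence from anesthesia using a Cox proportional hazards regression". The same sentence has this analysis adjust for the stratification variable. Proportional hazards is then checked by graph and by a treatment-by-log(time) interaction, with no threshold given. If the check fails: "In presence of an interaction the treatment effect will be assessed using the log-rank test from a Kaplan-Meier analysis".

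Three other places give context:

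- Protocol section: "Patients will be randomized 1:1, stratified for pre-operative chronic opioid use, with random-sized blocking to NOL guided analgesic management or routine care".
- Exploratory outcome 1, which also has a fallback model: "In either case we will again adjust for the stratification variable".
- Secondary outcome, where an estimate and interval are promised: "Results will be reported as the relative risk (95% CI) of having a" good pain score.

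No general rule elsewhere in the documents calls for estimates with intervals, or for stratified tests, across all outcomes.

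**The concern.** The switch loses two things at once. The Cox branch gives an adjusted effect size; the fallback, as written, gives an unadjusted p-value.

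A log-rank test is the score test of a Cox model that contains treatment alone. It remains a valid test that the two curves are equal, but it does not deal with the non-proportionality that triggered it. Its p-value mixes differences in centre and in spread. The hypothesis does not say whether faster refers to the median or the mean, so the p-value cannot say how much faster emergence is, or in which sense.

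Leaving out the stratification factor makes the test conservative if chronic opioid use affects emergence time, and some power is lost. What is at stake is the interpretation of one exploratory outcome. The stopping rules and the primary analysis are not affected.

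**Working it through.** The plan states no sample size, power, effect size or data for emergence time, so there is no figure to reproduce. Everything below is an illustration under assumed inputs.

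**1. The test by itself.** Assumptions: 144 uncensored patients (the planned maximum), Weibull times (shape 2, scale 10 min), 25% chronic opioid users, hazard ratio 1.6 for power, two-sided 0.05, 4,000 simulated trials. The log-rank test is applied in every trial, without waiting for the trigger.

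| Emergence time in chronic users | Null rejection: unstratified / stratified | Power: unstratified / stratified |
|---|---|---|
| no effect | 5.1% / 5.2% | 77.9% / 76.9% |
| 1.5 times as long | 4.2% / 5.6% | 70.2% / 78.4% |
| 2 times as long | 2.0% / 5.3% | 57.5% / 78.7% |

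So the unstratified test is conservative when the stratum matters. Stratifying costs about one point when it does not. These figures overstate the effect on the plan, because the fallback is used only after the trigger.

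**2. The whole plan (Cox first, log-rank if triggered).** Assumptions: 72 per arm; log-normal times; no censoring; medians of 10 min (routine) and 8 min (NOL) in patients without chronic use; 25% chronic users with log time shifted by 0.5, a factor of exp(0.5) = 1.65; trigger at |z| > 1.96 for the interaction; 4,000 trials per scenario. The gain is the trigger rate times the difference in rejection within triggered trials.

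| Log-SD routine, NOL | Trigger | Log-rank / stratified, triggered trials | Gain (points) | Whole plan: as written / stratified fallback |
|---|---|---|---|---|
| 0.5, 0.5 | 13.3% | 51.1% / 62.6% | 0.133 × 11.5 = 1.5 | 68.3% / 69.8% |
| 0.5, 0.6 | 48.8% | 27.3% / 34.4% | 0.488 × 7.1 = 3.5 | 34.2% / 37.7% |
| 0.6, 0.5 | 8.5% | 75.1% / 80.1% | 0.085 × 5.0 = 0.4 | 81.1% / 81.6% |
| 0.7, 0.4 | 80.9% | 93.1% / 96.0% | 0.809 × 2.9 = 2.3 | 94.1% / 96.5% |
| 0.8, 0.5 | 67.3% | 85.2% / 88.6% | 0.673 × 3.4 = 2.3 | 87.3% / 89.6% |

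The last column gives gains of 0.5 to 3.5 points; small differences from the product are rounding. Two scenarios with a much more variable NOL arm give 1.6 points (0.4, 0.7) and 1.2 points (0.5, 0.8). Under the null with equal spread, whole-plan type I error is 5.4% as written and 5.5% with stratification (Monte Carlo standard error 0.4 points).

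**3. What the missing estimate leaves open.** Take the routine arm as more variable (log-SD 0.7 against 0.4), with the same other inputs.

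- Medians 10 and 8: the true difference in restricted mean time up to 30 min is -3.44 min, and the log-rank is significant in 93% of triggered trials.
- Medians 10 and 10: the true restricted mean difference is -1.00 min, and the log-rank is significant in 27.5% of triggered trials.

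A significant log-rank result is compatible with either. An interval would help tell them apart. Across scenarios with the stratum effect, the stratified restricted mean difference had 95% CI coverage of 94.3% to 95.6% in triggered trials and a half-width of 1.9 to 2.3 min.

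**The case against.** The strongest reply is that this is a reporting preference in a low-stakes place. The branch is conditional and belongs to the third of six exploratory hypotheses. A Kaplan-Meier analysis is named, so curves and medians could be shown. The plan promises no interval for the primary outcome or for the Cox hazard ratio either, so silence on intervals is its usual style. Adjustment is stated earlier in the same paragraph, and a reader might carry it over. All of this limits the point, and the low rating stands. It does not remove it: the plan's models yield an estimate and interval when fitted, whereas a log-rank test does not. The text attaches the adjustment only to the Cox model, while the fallback for Exploratory outcome 1 states it for both branches.

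A reader might infer more than the documents support.

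- *That the fallback is invalid or inflates type I error.* It does not; see the null results above.
- *That the log-rank will often miss the effect or point the wrong way.* In one assumed case (log-SD 0.4 routine, 0.7 NOL, maximum N) the fallback triggers in 99% of trials, is significant in 6.5% of those, and disagrees in direction with the sample medians in 25%. That case needs a much more variable NOL arm. The Background says routine doses are often too small or too large and that over-dosed patients wake slowly; Specific Aims expects titration to bring doses close to what is needed. This suggests the reverse. With the spreads reversed, significance is 93% and disagreement 4%. Most of the 25% comes from non-significant results: in a separate run, a significant log-rank opposite to the medians occurred in 2 of 994 triggered trials (0.2%), and in 12 of 797 (1.5%) with the spreads reversed.
- *That the fallback will usually be used.* Trigger rates depend on N and on an assumed threshold. At 36 per arm, the second look, they fall to 8% (0.5, 0.5), 25% (0.5, 0.6), 8% (0.6, 0.5) and 53% (0.7, 0.4).

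**Conclusion.** The concern holds in a limited form. If the interaction is present, the plan replaces an adjusted hazard ratio with a log-rank test that, as written, omits the randomization stratum and yields no effect size.

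The impact is minor. The test is valid, and conservative only if chronic opioid use affects emergence time. The whole-plan power gain from stratifying is about 0.5 to 3.5 points, on assumed log-normal times, 72 per arm, a 25% stratum with a 0.5 log-time shift, and a 0.05 trigger. None of these inputs comes from the documents beyond the maximum N. The more useful gain is that the result would carry an effect size and an interval.

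**What to change.** Replace the fallback sentence with something like: *If the interaction is present, the groups will be compared by a log-rank test stratified by pre-operative chronic opioid use. The treatment effect will be reported as the stratified difference in restricted mean time to extubation, with 95% CI, up to a time limit fixed in advance.*

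Restricted mean time is an example. Another estimate that does not need proportional hazards and accounts for chronic opioid use would serve, such as a stratified difference in medians or a ratio of geometric means from regression of log time. One should be named before unblinding, because the candidates can disagree. With log-SD 0.7 routine and 0.4 NOL (medians 10 and 8), the restricted mean difference is significant in 90% of triggered trials and the geometric mean ratio in 60%; with mild or no inequality the order can reverse (76% and 89% at equal spread of 0.5).

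The cost is a sentence or two in the SAP and no new data, since Measurements already records "the time at which sevoflurane is discontinued, along with the end of surgery (last stitch), eye opening, and extubation". The downside is that the estimate targets one quantity, mean time, and may differ from the medians or the log-rank result. If the trial stops at the first look (36 patients), a 25% stratum would hold only 36 × 0.25 = 9 patients, so the SAP should also say how a sparse stratum is handled.

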### **Sample size justification.**

**Pilot patients:** N=21 pilot patients were enrolled prior to the start of the study to familiarize the study team with the protocol and identify any systematic issues that might result in protocol modifications. In the below sample size calculations we used data on these patients to help estimate the standard deviation of the primary outcome (pain score) and the within-subject correlation on the pain score across the 7 measurement times.

**Required Sample Size.** We plan the study to have 90% power at the 0.05 significance level to detect a difference in mean pain score of 1.25 or more between groups when measured over 10 minutes intervals during the first 60 minutes in the recovery period and analyzed using a linear mixed effects regression model. Based on our pilot study data (N=21) and previous work (SOLAR study report, Figure 1) we estimate the standard deviation of the pain score to be about 2.5 and the within-subject correlation to be approximately 0.60 when assumed to be exchangeable across measurements. Making these assumptions we would need a total of 116 patients before accounting for interim analyses, and a maximum of 144 after adjusting for planned interim analyses at each 1/4 of the maximum sample size. We therefore plan to randomize and enroll a maximum of 144 patients under these assumptions.

**Interim analyses.** We will conduct interim analyses for efficacy and futility at each 1/4 of the maximum sample size using a group sequential design and conservative gamma spending function parameters of -2 for efficacy and 0 (more aggressive) for futility. If the alternative hypothesis effect size (1.25 point difference) is true in the population sampled from, with the planned sample size we will cross an efficacy or futility boundary at each of the 4 looks with respective cumulative probabilities of 0.16, 0.50, 0.78 and 1.0.

Z-statistic boundaries for efficacy (futility) will be  $> 2.80$  ( $\leq 0.156$ ),  $> 2.58$  ( $\leq 0.667$ ),  $> 2.34$  ( $\leq 1.42$ ), and  $> 2.09$  ( $\leq 2.09$ ). The average total sample size across many simulations, assuming the alternative hypothesis is true (a true difference of 1), is N=64.

**Simulations with Effect Size Larger Than Planned.** With the given design and corresponding stopping rules, if the true effect size (difference of 1.25 in mean pain score) is large than planned, the probability of crossing an efficacy boundary earlier in the trial will be proportionately increased. For example, if the true difference is 1.5, the cumulative probability of crossing a boundary (either efficacy or futility) in the 1st through 4th looks will be approximately 0.21, 0.62, 0.91 and 1.0, with average total sample size across many simulations was 81 patients.

**Internal Pilot Study to Reassess Standard Deviation and Within-Patient Correlation.** At the second interim analysis we will conduct an internal pilot study to reassess the standard deviation and within-patient correlation using the observed data for the primary outcome. Without considering the observed treatment effect, in a blinded fashion, we will use the observed within-patient correlation from the linear mixed effects model and the standard deviation at each time point to reassess the maximum required N to have 90% power at the 0.05 significance level to detect a difference of 1.25 or more in pain score. If the required sample size is at least 10% higher than initially planned, the Executive Committee will decide whether to recommend that the maximum sample size be

increased to maintain 90% power. There is no statistical penalty for this internal pilot re-estimation of the within-patient correlation “nuisance parameter”.

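### The primary test is adjusted for four looks, but the plan names no estimate, confidence interval or p-value that allows for early stopping

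*Combined protocol and SAP*

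**What the plan says.** Under Sample size justification, the interim-analysis paragraph reads: "We will conduct interim analyses for efficacy and futility at each 1/4 of the maximum sample size using a group sequential design". It names gamma spending functions (-2 for efficacy, 0 for futility) and prints Z boundaries for efficacy (futility) of 2.80 (0.156), 2.58 (0.667), 2.34 (1.42) and 2.09 (2.09). The maximum is 144 patients, so the looks fall at 36, 72, 108 and 144.

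Under Data Analysis, the primary analysis is a linear mixed model: "We will assess the treatment effect of NOL guided analgesic management versus routine care on mean pain score". No format for the estimate, interval or p-value is given. The only effect interval promised in that section is for the secondary outcome: "Results will be reported as the relative risk (95% CI". Neither section links estimation to the stopping rule.

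**The concern.** Boundaries that allow for four looks control the error rate of the decision. They do not make the ordinary estimate unbiased, or the ordinary 95% interval a 95% interval, because the sample size at stopping depends on the data. The mixed-model coefficient is the only primary estimator described, so it is the natural default for the report.

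Two uses of the result are exposed. The Aim section judges the difference against a clinically meaningful 1 point. The Human Subjects Protection section says the trial will help design a Phase 3 study. If the method is chosen only after an early stop, the choice is also open to criticism.

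**Working it through.** **Inputs.** From Sample size justification: "We plan the study to have 90% power at the 0.05 significance level to detect a difference in mean pain score of 1.25 or more" and "we estimate the standard deviation of the pain score to be about 2.5 and the within-subject correlation to be approximately 0.60". From Data Analysis: 7 scores per patient. From Protocol: 1:1 allocation.

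**Reproducing the plan's figures.**
- SD of a patient's 7-score mean: 2.5 × √((1 + 6 × 0.60)/7) = 2.027 (variance 4.107).
- Fixed-sample N for 1.25 points, two-sided 0.05, 90% power: 56 per arm (112) with the normal formula and 57 per arm (114) with the noncentral t. With 6 scores the t version gives exactly 116. The plan states 116.
- Solving the stated spending functions (one-sided 0.025, non-binding futility) gives efficacy bounds 2.80, 2.58, 2.34 and 2.09, as printed, and an inflation of 1.221. Then 1.221 × 116 ≈ 142, against the stated 144.

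**Smallest difference that can cross at each look.** SE = 2.027 × √(2/n per arm).

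| Look | n per arm | SE | Bound | Bound × SE |
|---|---|---|---|---|
| 1 | 18 | 0.676 | 2.80 | 1.89 |
| 2 | 36 | 0.478 | 2.58 | 1.23 |
| 3 | 54 | 0.390 | 2.34 | 0.91 |
| 4 | 72 | 0.338 | 2.09 | 0.71 |

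The look-1 floor depends on the observed SE. Over an assumed range of SD 2.0 to 3.0 and correlation 0.4 to 0.8, it runs from 1.30 to 2.55.

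**Ordinary estimate ± 1.96 SE at the stopping look.** Simulation with the printed bounds, SE taken as known, both boundaries obeyed, 2,000,000 trials per scenario:

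| True difference | Mean estimate | Coverage | Efficacy stop at look 1 | Mean estimate of those |
|---|---|---|---|---|
| 1.25 | 1.37 | 91.5% | 17% | 2.25 |
| 1.0 | 1.04 | 92.8% | 9% | 2.21 |
| 0.5 | 0.35 | 92.8% | 2% | 2.14 |
| 0 | -0.18 | about 95% | – | – |

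Repeated runs put coverage at 1.25 between 91.5% and 91.6%. Among look-1 successes alone it is 85% at a true 1.25 and 73% at a true 1.0.

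**Where the misses lie at a true 1.25.** About 5.5% of intervals fall wholly below the truth and 2.95% wholly above, against 2.5% each nominally. The low misses cannot come from successes. The smallest upper limit for a success is at look 4: 0.71 + 1.96 × 0.338 = 1.37, which exceeds 1.25. They come from trials that did not cross for efficacy, mainly futility stops. If futility is never acted on, coverage is about 94.7%.

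**Early successes at a true 1.25.** Looks 1 and 2 together account for 53% of trials, with mean estimate 1.77. A later trial sized on 1.77 would have (1.25/1.77)² ≈ 0.50 of the patients needed for 1.25.

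**Last look.** With Z between 1.96 and 2.09 (a difference between 1.96 × 0.338 = 0.66 and 0.71), the ordinary 95% interval excludes 0 although the boundary is not crossed.

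**What adjusted methods give** (stage-wise figures with futility treated as non-binding).
- Look 1, on the boundary: ordinary 1.89 (0.57 to 3.22). The stage-wise result is essentially the same. The bias-adjusted estimate is 1.73, and the repeated confidence interval is 0.00 to 3.78.
- Look 3, Z = 3.0: ordinary 1.17 (0.41 to 1.93); stage-wise 1.08 (0.23 to 1.88).
- Look 4, Z = 2.7: ordinary 0.91 (0.25 to 1.57); stage-wise 0.82 (0.09 to 1.52).

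**The case against.** The efficacy boundaries reproduce and nothing here shows an error in the efficacy decision. Average bias is modest: 0.12/1.25, about 9%, at the design effect and 4% at the 1-point threshold. The choice among post-stopping estimators is partly a matter of preference. All of that stands, and it limits the point to estimation.

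A reader might infer more, in four ways that the documents do not support.
- **That the plan prescribes an ordinary 95% interval for the primary outcome.** It prescribes none; the defect is silence.
- **That the effect will be overstated in general.** At a true 0.5 the mean estimate is 0.35, an understatement. At a true 1.25, successes at looks 3 and 4 average 1.17 and 0.94, both below the truth.
- **That undercoverage reflects exaggerated success.** At 1.25 most of the excess misses are intervals that are too low. At 1.0 low misses (3.9%) also slightly outnumber high ones (3.4%).
- **That a look-1 success can never show less than 1.9 points.** That floor holds only if the observed SE matches the planning SE.

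**Conclusion.** The concern holds as an omission with measurable consequences. If the ordinary estimate and interval are reported, coverage is about 91.5% to 93% for true differences of 0.5, 1.0 and 1.25, and nominal at 0. Overstatement is concentrated in early efficacy stops. At the planning SE a first-look success must show nearly twice the 1-point clinically meaningful difference, even if the truth is 1.0 or 0.5.

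The figures assume SD 2.5, exchangeable correlation 0.60, seven scores, SE taken as known, and both boundaries obeyed as printed. The first futility bound is printed as 0.156, whereas the stated spending gives about -0.17, so a minus sign may be missing. Using -0.156 changes little at a true 1.25: mean estimate 1.38, coverage 91.3%.

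**What to change.** Before the first look, add to the Data Analysis section and the interim-analysis paragraph:

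1. The primary 95% confidence interval and p-value will come from stage-wise ordering, computed for the looks and sample sizes actually used (including any change after the planned sample-size reassessment). The ordinary estimate will be shown beside them. State whether futility is treated as binding.
2. Because stage-wise ordering leaves a first-look result unchanged, a bias-adjusted estimate or a repeated confidence interval will also be reported. Name which one in advance.
3. The secondary relative risk and its interval will be labelled as unadjusted for early stopping if the trial stops early.

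The cost is SAP wording and a standard group-sequential routine, with no change for patients or visits. The downside is a little more analysis work and a wider interval or smaller headline estimate after an early stop.
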